- Patients with a life expectancy of less than three years.
- Patients diagnosed with severe shoulder instability
- Patients diagnosed with subscapularis incompetence
- Patients with active medico-legal activity regarding the index shoulder
- Patients known to be pregnant, planning to get pregnant, a prisoner, and/or alcohol or drug abuser
- Patients known to be involved in worker's compensation litigations regarding index shoulder
- Patients with known metal allergy
- Patients who refuse to sign the IRB approved consent form.
- Patients who are found intraoperatively to require a specific treatment and are unable to be randomized

• Patients, found at the time of intraoperative examination to have a single cyst >1cm in size or multiple cysts at implantation site

NOTE: Patients with a previous total shoulder replacement of the contralateral shoulder are eligible for participation in the study. However, the patient and surgeon must allow for at least 9 months between procedures.

PATIENT POPULATION

A study population of 132 investigational shoulders and 132 control shoulders undergoing primary total shoulder arthroplasty for any of the diagnoses in the Inclusion Criteria will be included in this study. All patients, regardless of sex, race, or geographic location must meet all the eligibility criteria. All patients must sign an Informed Consent to be enrolled into the study. The study requires that bilateral patients must be staged so, a separate Informed Consent must be completed for each operative side.

INSTITUTIONS

A maximum of 17 investigational sites will enroll patients into the study.

DURATION OF THE STUDY

Patient recruitment is expected to take place over a period of 24 months and all patients are to be followed annually until the last patient enrolled reaches the 2-year follow-up time point. Therefore, some patients will be evaluated for 3-5 years post-operatively or longer, depending on the length of enrollment.

STUDY DEFINITIONS AND GLOSSARY OF ABBREVIATIONS

Withdrawal: Patients who die or who formally withdraw their consent (in writing) to additional follow up. Patients who have had all components removed or humeral stem components removed.

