It is possible that during the course of the study, certain changes may become desirable, although none are anticipated at this time. All changes to the investigation require prior approval from the investigator's Institutional Review Board (IRB) or Ethics Committee (EC) and if necessary, the FDA. Any other deviation from the stated protocol will be considered as such and will be reported accordingly. Since TSA is an elective procedure, it is not expected that treatment will require administration in an emergency setting, therefore all changes to the protocol require review and approval by the investigator's IRB prior to implementation.

RADIOGRAPHIC PROTOCOL

A detailed radiographic protocol is contained in Exhibit 3.

STATISTICAL ANALYSIS PLAN

This is a two-group, multi-center, randomized single blinded clinical trial to compare Total Shoulder Arthroplasty with Biomet's Comprehensive[®] Shoulder System with nano humeral component to another active intervention, a Total Shoulder Arthroplasty with Comprehensive[®] Shoulder System with mini stem component (abbreviations: Investigational vs. Control).

PRIMARY STATISTICAL HYPOTHESES AND DEFINITION OF STUDY SUCCESS

This study is designed to show that the Investigational device is non-inferior to the control device using three co-primary study endpoints. This will be shown using a closed testing method in which each of the primary endpoints specified below are compared using α =0.05. Study success requires that the Investigational group successfully demonstrate non-inferiority when compared to the Control group for all three of the individual primary endpoints, using the statistical methods described below. Because non-inferiority must be successfully shown for all three endpoints for study success, the type I error rate is preserved at 5% for the entire primary endpoint.¹

The individual non-inferiority hypotheses for each of these three tests are as follows:

Radiographic Success

The proportion of successful outcomes (i.e., patients meeting radiographic success criteria) in the Investigational group is non-inferior to the proportion of successful outcomes in the Control group using a 10% margin of non-inferiority. The test is based on the lower bound of a one-sided 95% confidence interval for the difference, Investigational minus Control, in proportions of success at 22+ months. A conclusion of non-inferiority is supported if the lower bound of the confidence interval is at least -0.10.

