Balanced, blocked randomization (1:1, Investigational: Control) will be implemented. Randomization will be per shoulder, and each shoulder will count as a separate case toward the total sample size. In the event that a screen failure occurs post-randomization, randomization will not be reassigned and this shoulder will not count toward the overall sample size. Randomization will continue with the next shoulder enrolled as previously described until the minimum sample size is reached in both treatment groups. Randomization will be blocked by site, and each site will receive separate randomization plans using a predetermined block size that will remain undisclosed to the sites.

SAMPLE SIZE CALCULATION INITIAL SAMPLE SIZE CALCULATIONS AND ASSUMPTIONS

The primary objective of this study is to show that the Investigational device is non-inferior to the Control device with respect to three co-primary endpoints at 22+ months. The sample size for each endpoint was calculated, and the largest chosen as the sample size for this study. The endpoint requiring the largest sample size was Radiographic Success; therefore the sample size for this study will be the one described immediately below. For reference, the sample size for the other two endpoints is shown as well.

Radiographic Success

Non-inferiority sample size calculations were implemented in nQuery Advisor 7.0 software using a 1:1 ratio of Investigational to Control subjects. This software uses methodology as described in a text by Farrington and Manning⁵.

The sample size needed to obtain 90% power for testing for non-inferiority of the investigational device to the control device with regard to radiographic success was calculated as follows:

⁵ Farrington and Manning. "Test statistics and sample size formulae for comparative binomial trials with null hypotheses of non-zero risk difference for non-unity relative risk". *Statistics in Medicine* 9(1990) pp 1447-1454.

Definitions:

 p_I : Proportion of Radiographic success in the Investigational treatment group

 p_C : Proportion of Radiographic success in the Control treatment group.

δ: Non-inferiority margin. Lower 95% confidence bound for difference in proportions of clinically successful subjects at 22+ months (Investigational – Control) must be greater than -δ.

For a specified constant, $0 < \delta < 1$, the hypotheses of non-inferiority are:

 $H_0: \ p_I - p_C \le -\delta \ vs. \quad H_A: \ p_I - p_C > -\delta.$

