Information on plausible values of the percentage of patients projected to be radiographic failures was found by looking in the literature to find plausible rates for each component of the radiographic failure definition. Subsidence and migration of the humeral component and progressive radiolucency around the humeral component have been reported at approximately 2% and 0%, respectively. Migration of the glenoid component and progressive lucency of the glenoid component have been reported at approximately 5% and 6%, respectively⁶. Because some overlap is to be expected, the overall Radiographic Success rate is estimated to be 93% for sample size calculation purposes.

Assumptions:

α = 0.05	Probability of Type I error
β = 0.10	Probability of Type II error: power = $1 - \beta$
$p_{C} = p_{I} = 0.93$	Estimated success rate for Control and Investigational groups
δ = 0.10	Non-inferiority Margin

⁶ Sperling,et al. "Radiographic assessment of ingrowth total shoulder arthroplasty." *JBJS.* November/December 2000, Vol 9 No. 6, p 507-513.

Resulting sample sizes (number of shoulders), not adjusted for attrition, are 112 Investigational vs. 112 Control (5% type I error rate, 90% power). The sample size was increased by 15% to allow for possible attrition. This gives a sample size of 264 total subjects (132 Investigational and 132 Control).

Absence of Revision/Removal/UADE

Non-inferiority sample size calculations were implemented in nQuery Advisor 7.0 software using a 1:1 ratio of Investigational to Control subjects. This software uses methodology as described in a text by Farrington and Manning⁷.

The sample size needed to obtain 90% power for testing for non-inferiority of the investigational device to the control device with regard to Absence of Revision/Removal/UADE was calculated as follows:

Definitions:

p_I : Proportion of shoulders in the Investigational treatment group without a

Revision/Removal/UADE

 p_C : Proportion of shoulders the Control treatment group without a Revision/Removal/UADE δ : Non-inferiority margin. Lower 95% confidence bound for difference in proportions of clinically successful subjects at 22+ months (Investigational – Control) must be greater than $-\delta$.

For a specified constant, $0 < \delta < 1$, the hypotheses of non-inferiority are:

$$H_0: p_I - p_C \le -\delta vs. \quad H_A: p_I - p_C > -\delta.$$

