Information on plausible values of the percentage of patients with a revision was found in an article by Jost, et. al. on subjects with Biomet Comprehensive mini-stem shoulder device⁸. A

⁷ Farrington and Manning. "Test statistics and sample size formulae for comparative binomial trials with null hypotheses of non-zero risk difference for non-unity relative risk". *Statistics in Medicine* 9(1990) pp 1447-1454.

total of 49 patients underwent shoulder replacements with the TESS humeral prosthesis with minimum follow-up 2 years. One implant was revised, resulting in a revision rate of 2.0%.

Fracture/perforation of bone, joint dislocation, and dissociation of the device have been reported at approximately 2%⁹, 1%¹⁰ ¹¹, and 0¹²% respectively. Fracture/perforation of the device is not expected to occur and so is estimated at 0%, Using this information, overall success rate is estimated to be 95% (2%+2%+1%) for sample size calculation purposes.

Assumptions:

$\alpha = 0.05$	Probability of Type I error
β = 0.10	Probability of Type II error: power = $1 - \beta$
$p_{C} = p_{I} = 0.95$	Estimated success rate for Control and Investigational groups
δ = 0.10	Non-inferiority Margin

Resulting sample sizes (number of shoulders), not adjusted for attrition, are 82 Investigational vs. 82 Control (5% type I error rate, 90% power). The sample size was increased by 15% to allow for possible attrition. This gives a sample size of 194 total subjects (97 Investigational and 97 Control).

⁸ Jost, Patrick et. al. "Total Shoulder Arthroplasty Utilizing Mini-Stem Humeral Componts: Technique and Short-Term Results." *Hospital For Special Surgery Journal* (2011).

⁹ Bohsali, et. al. "Complications of Total Shoulder Arthroplasty." *JBJS.* 2006 Volume 88-A Number 10, p 2279-2292.

¹⁰ Pfahler, et. al. "Hemiarthroplasty versus total shoulder prosthesis: Results of cemented glenoid components." *J Shoulder Elbow Surg* March/April 2006, p 154-163.

¹¹ Boyd, et. al. "Total Shoulder Arthroplasty vs Hemiarthroplasty." *Journal of Arthroplasty*. December 1990, Vol 5 No. 4, p 329-336.

¹² Blevins, et. al. "Dissociation of modular humeral head components: A biomechanical and implant retrieval study." J Shoulder Elbow Surg March 1997, Volume 6 Issue 2, p A1.

American Shoulder and Elbow Surgeons(ASES) Score

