The association between the primary endpoints and device group at 22+ months across investigators will be examined using either an analysis of variance model (for ASES score) or the Breslow-Day test for homogeneity of odds ratios (for Radiographic Success and Absence of Revision/Removal/UADE). These tests for interaction will use a p-value of 0.10. If there is no evidence of treatment *center interaction ($p \ge 0.10$) for a particular outcome, data will be pooled across centers for that outcome. If p < 0.10, then this outcome for each site will be examined graphically to assess site dependency as well as whether or not a qualitative interaction exists. Further, the sites contributing to this interaction will be examined, and if necessary, a stratified analysis will be conducted and results compared to overall study results to assess consistency.

In addition, the association between device group and the primary endpoints for unilateral and bilateral subjects will be examined using either an analysis of variance model (ASES) or the Breslow-Day test for homogeneity of odds ratios (Radiographic Success and Absence of Revision/Removal/UADE). As before, a significant p-value (p <0.10) for a particular outcome indicates heterogeneity in that outcome for unilateral and bilateral subjects; if this occurs, that outcome for each group will be examined graphically and descriptively to assess these differences. Primary outcomes for unilateral and bilateral subjects will also be compared using a Fisher's exact test (Radiographic Success and Absence of Revision/Removal/UADE) or a pooled t-test (ASES). If p<0.10 for the two-way comparison or the test for interaction, the

bilateral subjects will be compared as a separate group for that outcome, and additional unilateral subjects may be enrolled (via IDE supplement/protocol amendment) in order to protect statistical power of the primary study analysis.

PROTOCOL DEVIATIONS

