A description of all protocol deviations will be provided. The association between the proportion of subjects with a protocol deviation and device group across investigators will be examined using the Breslow-Day test for homogeneity of odds ratios. Investigators with less than or equal to 3 cases in either treatment will be combined to form a "pooled" investigator for analysis. A significant p-value indicates heterogeneity of odds ratios for the proportion of subjects (Investigational vs Control) with a protocol deviation across investigators, and in this case the proportions of subjects with a deviation will be examined graphically and descriptively by treatment group and site to assess dependency.

DATA COLLECTION

DATA COLLECTION TIME POINTS

Windows for this study will be as follows:

Table 1: Analysis Windows

Interval	Follow-Up Window
	(Days from Surgery)
Preoperative	≤ 0
6 Weeks	28-56
3 Months	78-106
1 Year	304-426
2 Year	669-791
2+ Year	> 791

The principal data collected is described in the following table:

Study Parameter	Data Collected
Demographic and Baseline Measurements	Age, Height, Weight, Gender, Race/Ethnicity, Unilateral/Bilateral, Primary Diagnosis, Prior Treatments, Concomitant Medications
Efficacy Measurements	American Shoulder and Elbow Surgeons (ASES) Score, Constant Score, SANE Score, Radiographic Assessment
Safety Measurements	Revision/Removal, Adverse Events
Study Success Criteria	Study success requires that the Investigational group successfully demonstrate non-inferiority when compared to the Control group for all three of the individual primary endpoints.

Table 2: Principal Study Data

INFERENTIAL METHODS

SIGNIFICANCE LEVELS

The Type I error rate for the primary study analysis will be 0.05.

Comparisons for secondary, exploratory, and safety analyses will use $\alpha = 0.05$, with no adjustment for multiple comparisons. Because no adjustments will be made for multiple

comparisons, secondary, exploratory, and safety endpoints will be reported as exploratory analyses without claims of statistical significance.

SUBJECT ACCOUNTING

Accountability tables will be generated to show, at each study visit, the number of Investigational and Control subjects who might be expected to attend a given visit and the number and proportion who did attend.

The following definitions specify how the subject accountability table tracks subject follow-up for the Control and Investigational arms:

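### A p<0.10 test on the 22+ month outcomes can change which shoulders enter the primary test and reopen enrolment, and the stated 5% type I error does not allow for this; the inflation is modest

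*Combined protocol and SAP*

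**What the plan says.** Tests for Interaction sets two tests of unilateral against bilateral shoulders for each co-primary endpoint. One is a device-group interaction test (analysis of variance for ASES, Breslow-Day for the two binary endpoints). The other compares unilateral with bilateral outcomes directly (pooled t-test or Fisher's exact test) and ignores device group. If either has p<0.10, the bilateral shoulders are compared separately for that outcome, and "additional unilateral subjects may be enrolled (via IDE supplement/protocol amendment) in order to protect statistical power of the primary study analysis". The section gives no number to add, no timing, no statement on whether non-inferiority has already been tested, and no error rule for a later test.

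Under Primary Statistical Hypotheses and Definition of Study Success, all three endpoints must pass, and for that reason "the type I error rate is preserved at 5% for the entire primary endpoint". Significance Levels adds: "The Type I error rate for the primary study analysis will be 0.05". For the binary endpoints, "The test is based on the lower bound of a one-sided 95% confidence interval"; ASES is handled in the same way with a 9.5-point margin.

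On timing, Duration of the Study says "Patient recruitment is expected to take place over a period of 24 months", with follow-up until the last enrolled patient reaches two years. The Bilateral Patients section requires at least 9 months between a patient's two study procedures.

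**The concern.** The clause aims to protect power, but its trigger is computed from the primary outcomes, and one of its two tests uses them by arm. This has two consequences.

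First, the analysis set for an endpoint is chosen after its data are seen. The section does not spell out that the primary test then uses unilateral shoulders only. However, adding unilateral shoulders to protect the power of that test makes sense only if the bilateral ones have left it.

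Second, enrolment may be reopened when comparative results are available. Nothing in the text says that non-inferiority must not yet have been tested, or that it may be tested only once. If a failed unilateral test were followed by more shoulders and a second test at the same level, the chance of wrongly accepting an inferior device would exceed 5%. The stated justification for 5% deals only with having three endpoints.

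**Working it through.** **1. The plan's own sample size.** For the binary endpoints, n per arm = (z₀.₉₅ + z₀.₉₀)² × 2p(1−p)/δ², with (1.645 + 1.282)² ≈ 8.56.
- Radiographic success ("the overall Radiographic Success rate is estimated to be 93% for sample size calculation purposes", margin 0.10): 8.56 × 2 × 0.93 × 0.07 / 0.01 ≈ 111.5, so 112. Dividing by 0.85 gives 132.
- Absence of revision/removal/UADE (0.95): 8.56 × 2 × 0.95 × 0.05 / 0.01 ≈ 81.4, so 82, then 97.
- ASES (SD 19, margin 9.5): 69 by the normal formula and 70 by the t distribution, then 83.

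All agree with the plan, so 112 evaluable shoulders per arm is used below.

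**2. When the tests can be run.** A second study shoulder is operated on at least 9 months after the first, so its earliest 22-month outcome is at month 9 + 22 = 31, after the expected 24 months of recruitment. The full data set is available at month 24 + 22 = 46.

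**3. How often the trigger fires by chance.** Two independent tests at 0.10 give 1 − 0.9² = 0.19. Simulated for ASES at the margin, the rate is about 18%. For radiographic success it is about 12–17%.

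**4. Error for one endpoint (ASES).** Monte Carlo with a true difference of −9.5, SD 19, 112 per arm and independent shoulders. Non-inferiority is accepted if (x̄_I − x̄_C) − 1.645 √(s_I²/n_I + s_C²/n_C) ≥ −9.5, which is the bound under Efficacy Evaluations with the sign reversed. The documents do not give the number of bilateral shoulders. It is assumed to be 6, 11 or 22 per arm (6/112 = 5%, 11/112 = 10%, 22/112 = 20%). In triggered trials the unilateral shoulders are tested alone. In the last two columns, a failure is followed by added unilateral shoulders and a retest at an unadjusted 5%. The figures come from 100,000 runs per row.

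| Bilateral per arm | Switch only, all trials | Fail, top up, retest: all trials | Fail, top up, retest: triggered trials |
|---|---|---|---|
| 6 | 5.2% | 5.4% | 7.3% |
| 11 | 5.5% | 5.7% | 8.4% |
| 22 | 5.5% | 5.9% | 10.1% |

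A separate run of 300,000 trials gives 5.1/5.3/5.7% for the switch alone and 5.3/5.5/6.0% with the retest, so the two runs agree within 0.2 percentage points. In that run, a top-up followed by one final test gives 5.1/5.2/5.5%, no higher than the switch alone. Varying the number added from one times the bilateral count up to 112 per arm keeps the retest figure within 5.3–6.1%.

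**5. Radiographic success** (0.93 against 0.83, Wald bound, same rule). A single test gives 5.2–5.8%. With the retest it is 5.6–6.6% overall and 6.1–12.9% in triggered trials. The part of the single-test error above 5% comes from the Wald bound and is a separate matter.

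**6. Calendar.** Recruitment runs at 264/24 = 11 shoulders per month. Adding 12 to 44 shoulders takes 12/11 = 1.1 to 44/11 = 4 months. The second readout is then at month 46 + 1.1 + 22 ≈ 69 to 46 + 4 + 22 = 72, about two years later, before any regulatory time.

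**The case against.** The strongest reply is that this is a contingency with a legitimate aim and an external gate. Separating bilateral shoulders would cost power. With 106, 101 or 90 shoulders per arm left, radiographic power is Φ(0.10/√(2 × 0.93 × 0.07/n) − 1.645), or about 89%, 87% or 84% against the planned 90%. Any addition needs an IDE supplement or amendment, and Anticipated Changes requires IRB approval and, if necessary, FDA approval. The number added and the error control could be settled at that stage. All of this stands, but the gate does not repair the statistics: the sponsor would propose the extension when arm-level outcomes are available. Nor does power require an outcome-based trigger, because the count of bilateral shoulders is known during recruitment.

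Four stronger readings are tempting, and the documents do not support them.
- A reader might infer a built-in second attempt at non-inferiority. The trigger is heterogeneity, not a failed test. Fail-then-retest is allowed by silence, not prescribed.
- A reader might infer that reopening cannot fit the study duration. The Study Summary and Duration of the Study tie the end to the last patient enrolled, and the 24 months is only an expectation. No fixed end date is breached.
- A reader might blame reopening for all the inflation. Much of it comes from the switch to unilateral shoulders, and a top-up with one final test adds nothing further.
- A reader might take 1 − 0.9⁶ = 47% as an upper bound on the trigger over six tests. It is the value under independence; the bound is 6 × 0.10 = 60%. The rule also applies outcome by outcome, so neither figure gives the error for one endpoint.

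**Conclusion.** The point holds in a limited form. The primary analysis set, and optionally further enrolment, depend on outcome-based tests that cannot be completed until after the expected recruitment period. The 5% statement covers neither the data-driven switch nor a repeat test. For ASES, one-endpoint error rises from 5% to about 5.2–5.5% from the switch alone. It reaches about 5.4–5.9% under the least favourable use modelled, and about 7–10% within the roughly 18% of trials where the trigger fires.

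These figures assume no true heterogeneity, independent shoulders and a bilateral share of about 5–20%, which the plan does not give. They affect study success only when the other two endpoints pass. The inflation is modest and the remedy is simple, so this is a cheap improvement and not a flaw that undermines the trial.

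**What to change.** In Tests for Interaction:
1. Delete the outcome-triggered option to enrol additional unilateral subjects.
2. State that the primary non-inferiority test is done once, on all shoulders in the Analysis Population, whatever the heterogeneity tests show.
3. Report the unilateral and bilateral results as supportive.
4. Let any top-up depend only on the count of bilateral shoulders, without outcome data, and decide it before recruitment closes.

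If the option is kept, fix the number to be added. Require either a single final non-inferiority test after the added shoulders reach 22+ months or an alpha-controlled procedure, and restate the type I error accordingly. A single final test removes the retest but leaves the small effect of the switch (about 5.1–5.5% in step 4).

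The cost is SAP wording. The sponsor gives up the post-outcome extension and the automatic separation of bilateral shoulders in the primary test; any real difference between the two groups would appear in the supportive results.

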Complete eligibility checklist	x					
Complete Patient History Form: HX100	x					
Complete ASES Assessments: ASES100	x		х	x	х	х
Complete SANE Assessment: SANE100			x	x	x	х
Complete Constant Score Form: CST100	х		X**	x	х	х
Randomize Patient		х				
Record Operative Details: OP100		х				
Collect Radiographic Images (AP Int., AP Ext, and Axillary Views)			x	x	x	x
Protocol Deviation Form: PD100	As needed	As needed	As needed	As needed	As needed	As needed
Complete Adverse Event Form: AE100 and/or Serious Adverse Event SAE100	As needed	As needed	As needed	As needed	As needed	As needed
Complete patient Withdrawal Form: WD 100		As needed	As needed	As needed	As needed	As needed
Complete Device Revision/Removal: RR100			As needed	As needed	As needed	As needed

Each follow-up visit time point will be determined based on the date of surgery.

** At the 6 week interval, in order to protect the subscapularis repair, the strength and ROM sections are not to be completed by sites.

*** Annual follow up will continue until study closure or until the last enrolled patient reaches their 2 year follow up window.

BILATERAL PATIENTS

A patient undergoing staged bilateral surgery must sign a consent form **for each study procedure**. Each study shoulder will be randomized separately. Bilateral patients will be required to wait at least 9 months between procedures for the purposes of the study.

Patients with staged bilateral study implants will require two ASES, Constant Score, and SANE assessment forms to allow individual assessment of each operative side over the course of the study. Patients must be instructed to assess each shoulder individually, i.e., only record right-shoulder pain levels on the CRF for their right shoulder and only report left shoulder pain on the CRF for the left shoulder.

SCHEDULE OF FOLLOW-UP ASSESSMENTS

Post-operative clinical and radiographic evaluations will be performed according to the following schedule, with the associated visit windows:

- 6 weeks (± 2 weeks)
- 3 months (± 2 weeks)
- 1 year (± 2 months)
- 2 years (± 2 months)
- Annually thereafter* (± 2 months)
- * Until all patients reach the 2-year visit window or the study is closed

ASSESSMENT PARAMETERS AND METHODS

Pre-Operative Visit - Medical History, Demographic Data and Patient Eligibility

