Theoretically Due: The number of implants that could be examined if all subjects returned on the first day of the follow-up window based on their respective initial surgery dates and the date of database closure.

Deaths: The number of deaths that have taken place in the course of the investigation according to scheduled follow-up visits.

Revisions: The number of revisions that have taken place in the course of the investigational study recorded according to the scheduled follow-up visit.

Withdrawal of Consent: The number of subjects that have withdrawn during the course of the investigational study recorded according to the scheduled follow-up visit.

Not Yet Overdue: Subjects in this category are those who have not yet been evaluated but who are still within the evaluation time window at the time of database closure.

Actual^A: The number of subjects with complete data (i.e. all primary outcomes can be determined) who are actually evaluated within the protocol-defined follow-up intervals.

Actual^B: The number of subjects with any follow-up data (in- or out-of-window) reviewed or evaluated by investigator ("all evaluated" accounting).

Expected: This element is the number of subjects expected for a given time interval. These include the theoretical number of subjects who are due to be evaluated, less the number of subjects who have died, withdrawn, been revised, or are not yet overdue in this time interval.

Follow-up Rate: This element is the ratio of actual subjects evaluated to expected subjects, expressed as a percentage.

MODELS FOR CONTINUOUS MEASURES

Comparisons of Investigational vs Control with regard to continuous baseline and secondary outcomes will be performed using standard statistical tests and will be chosen as appropriate for the scale and distribution of the measures being analyzed. A t-test, Wilcoxon test, or oneway ANOVA (as appropriate) will be performed to assess differences.

CATEGORICAL DATA ANALYSES

Comparisons of Investigational vs Control with regard to categorical baseline, secondary and safety outcomes will be performed using standard statistical tests and will be chosen as appropriate for the scale and distribution of the measures being analyzed. Specifically, categorical outcomes will be compared for investigational and control groups using the Fisher's Exact test (for 2x2 tables) or the Likelihood Ratio chi-square test (for tables larger than 2x2).

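### Under the open-ended 2+ Year window in SAP Table 1, missed annual visits cannot lower the follow-up rate reported after 2 years

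*Combined protocol and SAP*

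**What the plan says.** Four elements of the SAP's Subject Accounting section fix the rate for each interval, by arm.

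- Theoretically Due is "The number of implants that could be examined if all subjects returned on the first day of the follow-up window", given each surgery date and the date of database closure.
- Not Yet Overdue covers "those who have not yet been evaluated but who are still within the evaluation time window at the time of database closure".
- Expected is the number due, "less the number of subjects who have died, withdrawn, been revised, or are not yet overdue in this time interval".
- Follow-up Rate is "the ratio of actual subjects evaluated to expected subjects, expressed as a percentage".

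Two numerators are defined. Actual(A) is "The number of subjects with complete data (i.e. all primary outcomes can be determined) who are actually evaluated within the protocol-defined follow-up intervals". Actual(B) is "The number of subjects with any follow-up data (in- or out-of-window) reviewed or evaluated by investigator". The Follow-up Rate entry does not say which one it uses.

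SAP Table 1 (Analysis Windows, under Data Collection Time Points) gives closed day ranges for every postoperative interval up to 2 Year (669-791). Its last row, 2+ Year, is day > 791 with no upper limit. The protocol's Schedule of Follow-up Assessments, by contrast, gives each later visit a closed window: "Annually thereafter* (± 2 months".

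**The concern.** Not Yet Overdue is meant to spare a shoulder that still has time to attend. That works only if the window closes. In a window with no end, a shoulder that has missed its visit looks the same as one whose visit is still to come, and both are removed from Expected. Nobody can become overdue in the 2+ Year row.

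This row covers all the annual follow-up after the 2-year visit. It also takes in late attenders, whose evaluations after day 791 can supply data for the 22+ month endpoints. A reader would use its follow-up rate to judge how fully each arm was observed late, for example when reading the time-to-revision curves. The rule also sits badly with the protocol's own terms. Study Definitions and Secondary Endpoints class patients who cannot be located, or who fail to return for several consecutive visits, as missing data. In this row the same patients would be listed as Not Yet Overdue.

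**Working it through.** The documents state no follow-up rate, so there is none to reproduce. What can be reproduced is how SAP Table 1 was built.

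**1. Table 1 against the protocol schedule.** The day ranges are the scheduled visits converted to days:

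- 6 weeks ± 2 weeks: 42 ± 14 = 28-56
- 3 months ± 2 weeks: 92 ± 14 = 78-106
- 1 year ± 2 months: 365 ± 61 = 304-426
- 2 years ± 2 months: 730 ± 61 = 669-791

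All four match. The same conversion of the later annual visits gives 1095 ± 61 = 1034-1156, 1460 ± 61 = 1399-1521 and 1825 ± 61 = 1764-1886. Table 1 has a single open row in their place.

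**2. The rate in the open row.** Let D be shoulders theoretically due, X those subtracted for death, withdrawal or revision, E those evaluated, and U those neither evaluated nor in X. With no upper limit, Not Yet Overdue = U, so Expected = D − X − U.

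- If no evaluated shoulder is in X, then D − X = E + U, Expected = E, and Actual(B)/Expected = E/E = 100% for any U > 0 that leaves E > 0.
- If a share i of evaluated shoulders has incomplete data, Actual(A)/Expected = 1 − i, again whatever U is.
- If x evaluated shoulders later die, withdraw or are revised within the interval, and stay in Actual, then Actual(B)/Expected = E/(E − x), which exceeds 100%.

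**3. Numbers.** Illustrative assumptions: 264 shoulders, uniform accrual over 24 months, closure when the last shoulder reaches 2 years, visits missed at random, and no deaths, withdrawals or revisions. The Actual(A) column assumes 10% of evaluated shoulders are incomplete.

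| Missed | Due | Not Yet Overdue | Expected | Actual(B) rate | Actual(A) rate |
|---|---|---|---|---|---|
| 0% | 241 | 0 | 241 | 100% | 90.0% |
| 10% | 241 | 24 | 217 | 100% | 89.9% |
| 25% | 241 | 60 | 181 | 100% | 90.1% |
| 50% | 241 | 120 | 121 | 100% | 90.1% |
| 90% | 241 | 217 | 24 | 100% | 91.7% |

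The small movement in the last column is rounding to whole shoulders. At 100% missed the rate is 0/0. If instead 3% of evaluated shoulders are later subtracted, the Actual(B) rate is 102.8-104.3% at every miss rate from 0 to 90%.

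**4. Contrast with closed windows, same assumptions.** The 2 Year row gives 238/261 = 91.2%, 198/261 = 75.9% and 132/249 = 53.0% at 10%, 25% and 50% missed. A closed 3-year row gives 139/148 = 93.9%, 116/143 = 81.1%, 77/130 = 59.2% and 15/112 = 13.4% at 10%, 25%, 50% and 90% missed. The 3-year run used days 1035-1157, one day later than the conversion in step 1. Both closed rows respond to missed visits.

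**5. Three records at closure.** Shoulder (i) is at day 1300 and missed its 3-year visit. Shoulder (ii) is at day 800, with no annual visit open until day 1034. Shoulder (iii) is at day 1100 and attended its 3-year visit. Neither (i) nor (ii) has been seen since day 791. Under Table 1, three are due, two are Not Yet Overdue, Expected = 1 and the rate is 1/1 = 100%. On the annual schedule (ii) is not yet due, and the rate is 1/2 = 50%.

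**6. How many shoulders are involved.** With uniform 24-month accrual and closure when the last shoulder is at 22 or 24 months, the share past day 791 is 0.834 or 0.917 (about 220 or 242 of 264). The share that has reached day 1034 is 0.501 or 0.585, and the share past day 1156 is 0.334 or 0.418. About a third of all shoulders (0.834 − 0.501, or 0.917 − 0.585) are past day 791 with no annual visit open yet. Any of them not seen since day 791 are counted in Not Yet Overdue with those that missed a visit.

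**The case against.** The strongest reply is that Table 1 may not govern the accountability table. It is titled as analysis windows, the accountability tables are to be shown for each study visit, and Actual(A) refers to intervals defined by the protocol. If accountability ran on the annual visits in the protocol schedule, the windows would be closed and the problem would disappear. That reading is possible but less natural. The SAP introduces Table 1 as setting the windows for the study, its column heading uses the same term as the Theoretically Due definition, and the SAP does not point Subject Accounting back to the protocol schedule. If the annual windows were intended, the remedy is still to state them.

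Other objections stand and limit the point.

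- A reader might infer that the rate is always exactly 100%. The documents do not support that. It depends on the numerator, which is unstated, and on whether evaluated shoulders are later subtracted.
- Counting a shoulder as due from day 792, before its next annual visit opens, does not bias the rate. If unevaluated, it is removed again as Not Yet Overdue. Only the intermediate counts are affected.
- Missed visits are not wholly hidden. They sit in the Not Yet Overdue count for each arm, but mixed with shoulders not yet scheduled.
- A reader might infer that the co-primary comparisons are compromised. They are not. Missing primary data are defined separately, by whether the endpoint can be determined, and have their own sensitivity analyses. A shoulder unevaluated after day 791 already counts as overdue in the 2 Year row.

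**Conclusion.** The point holds as a reporting error after 2 years. Under SAP Table 1 and the Subject Accounting definitions as written, the 2+ Year follow-up rate does not respond to missed annual visits. That follows from the definitions and needs no assumption about accrual or attendance. Exact 100% requires Actual(B) as numerator and no later subtraction of evaluated shoulders. Moreover, a shoulder seen once after day 791 counts as evaluated for the whole row, even if it misses every later annual visit.

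The share of shoulders in the row (about 83-92%) and the share whose 3-year window has closed (about 33-42%) rest on uniform 24-month accrual and closure with the last shoulder at 22 to 24 months. The miss rates are illustrative, since the documents give none. The 2 Year row works as intended, and no hypothesis test, analysis population or success rule uses the rate. What is lost is a usable figure for the completeness of late follow-up in each arm, including any difference between arms. The change is worth making because it is cheap, but it has little bearing on the co-primary tests.

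**What to change.** For accountability, replace the single 2+ Year row with the annual windows already in the protocol schedule, converted as the earlier rows were: 3 Year 1034-1156, 4 Year 1399-1521 and 5 Year 1764-1886. Apply Theoretically Due, Not Yet Overdue and Expected to each row separately. Report the Follow-up Rate for both Actual(A) and Actual(B), by arm. Keep day 669 or later as the data rule for the 22+ month endpoints, so that the primary analysis is unchanged.

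The cost is SAP table wording and minor programming. It needs no new data and changes no test or sample size. The reported late follow-up rate may be less favourable.
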